1.2. The shape bias in Late Talkers

Late Talkers are infants that show a limited expressive language characterized by less than 50 words by the age of 2 in the absence of a physiological, cognitive or genetic disorder that may

account for this delay (Macroy-Higgins & Montemarano, 2015; Rescorla, 2011; Weismer et al., 2013). Late Talkers tend to be below the 15th percentile of expressive vocabulary (Colunga & Smith, 2008) and represent from 10% to 15% of the total infant population (Tsybina & Eriks-Brophy, 2007). Some of these infants “catch up”, but others show persistent language difficulties throughout their lives.

Interestingly, Late Talkers do not exhibit a shape bias (Colunga & Sims, 2011; Weismer et al., 2013). This might contribute to their language delay and to their difficulty of adding new words to their vocabulary, even though this is unlikely the only cause of their language delay. A family history of language delay and limited interaction between parent/guardian and infant are likely other important factors (Girolametto, Weitzman, & Earle, 2013).

The three conventional approaches followed for Late Talkers are ‘wait and see’, ‘watch and see’, and ‘early intervention’. The ‘wait and see’ approach means no action or intervention, and it is advised to wait until the infant is older to see whether a language delay is indeed present (Girolametto et al., 2013). The ‘watch and see’ approach consist of monitoring the infant’s language development and evaluate it every 3 to 6 months (Preston et al., 2010) to assess if intervention is required or if the infant “catches up”. The ‘early intervention’ approach consists of actively working with the infant to help them to develop their language.

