4.3. Tests and procedure of intervention programme

4.3.1. Vocabulary and developmental assessments. At session 1, parents/guardians will fill in a socioeconomic and general development questionnaire (see Appendix 1.5). The

information provided in this questionnaire will double-check the inclusion/exclusion criteria. It will also be used to check whether the intervention was only successful in a sub-group of the infants (e.g. those without a family history of language problems). In the first and last session, parents/guardians will also be asked to fill in the UK-CDI Words and Gestures questionnaire, a vocabulary checklist of words and phrases that infants might know and use (Alcock, Meints, & Rowland, 2017; see Appendix 1.4). This will allow us to compare language development during the intervention programme between the two intervention groups.

4.3.2. Initial cognitive assessments: The initial cognitive assessments will be presented during the first two sessions. During week 1, infants will be assessed with a shape sorting task and an attention task. The sorting task will last no more than 5 minutes and will be used to assess if before the training programme, infants are sensitive to the shape of objects and can group objects by shape. Infants will be presented with 16 novel objects differing in shape, colour and texture and asked to sort them into groups. How to sort (namely by shape) will be shown to them with the means of examples. The attention task will last 3 minutes and will assess infants' joint and sustained attention. This will be achieved by monitoring their eye movements during the presentation of five short video clips (35 seconds each) of a person looking at and moving unusual novel objects. For this task, participants will sit on their parent/guardian's lap in front of a computer screen. Eye movement will be monitored with a remote eye tracker (see Figure 2). The parent will wear blacked-out glasses so that their behaviour cannot affect the infants' eye gazes.

At week 2, infants' visual spatial abilities and working memory will be assessed using the Wechsler Preschool & Primary Scale of Intelligence - Fourth UK Edition (WPPSI-IV UK). This test will last about 20 minutes and will be used to rule out any potential cognitive delay.

Figure 2. Attention task. Infants will watch five short videos and eye movements will be monitored with a remote eye tracker.

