4.4. Procedure of follow up study

A follow up study will be conducted one year after the start of the intervention programme in order to assess the long-term effects of the intervention in language and cognitive development. For this follow up study children's language, and cognitive abilities, will be assessed. The British Picture Vocabulary Scale (BPVS3) will be used to assess receptive language. In this test the child will listen to a word and will have to select from a set of pictures, the image that corresponds to that word. The Wechsler Preschool & Primary Scale of Intelligence - Fourth UK Edition (WPPSI-IV UK) will be used to assess infant's visual spatial skills and working memory. In this test, the child will be asked to recreate different figures using blocks and to view animal cards on a zoo layout for a specified time, remember where they are located, and then place each card in the previously viewed location.

5. Ethical considerations

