6.3.1 Summary of baseline data

From the total number of assessments and tasks, results from five of them will be used as baseline data or descriptive statistics. These five assessments are: Vocabulary checklist, Socioeconomic and general development questionnaire, attention task, sorting task, initial working memory assessment, and initial visual spatial abilities assessment. The description of the variables analysed on each assessment and how they will be reported is as follows.

- A. Vocabulary assessment: Parents will fill out this checklist before (and after) the intervention and the total number of words that the infant understands and the total number of words they

produce will be registered as continuous variables and will be considered as the baseline language ability before the intervention programme.

- B. Socioeconomic and general development questionnaire: This questionnaire will provide information regarding general child development, language delay family history, and family status. A number of different types of variables will be collected: nominal variables (e.g. occupation) and ordinal variables (e.g. infant's order of birth). These variables will be used for descriptive statistics. They are potentially interesting as predictor variables, but the sample size is likely too small to draw any strong conclusions.
- C. Attention measure: With this measure, we will assess the fixation duration (number of milliseconds an infant looks) towards a novel object that is moved. The object will be moved for 25 seconds (25000 ms) and the infant's total looking time towards the screen will be registered. This variable will be registered as a continuous variable and used as a predictor of the primary outcome measures.
- D. Sorting task: This will be registered as a categorical variable. Infants will sort objects and depending on their sorting tendency they will be assigned to one of four categories: preference for shape, preference for colour, preference for texture, no preference. This variable will be used as a predictor of the primary outcome measures.

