6.3.2 Primary outcome analysis

During weeks 8 and 9 of the study infants will be assessed with two forced choice tasks where they will have to extend object names to new exemplars based on visual commonalities. We will assess the statistical difference between the response pattern and chance (using t-tests). This will show whether infants have learned to extend object names by shape similarities. The factors that predict the number of noun extensions based on shape as well as vocabulary growth will be assessed using mixed effect model analyses. The most important factors tested in the models will be the number of words known before the intervention, the intervention type (shape training vs specific word training), attention measures (pre-test and attention during training), and sorting task measure. The outcome of these analyses will show whether the shape bias intervention has led to a larger vocabulary growth than the specific word intervention (as a control intervention). It will also assess the role of attention in word learning and whether only infants that pay attention to novel items

presented to them or infants that are sensitive to shape similarities between objects can acquire a shape bias. Only data of infants that complete the intervention will be analysed.

Regarding the follow up study, infants' vocabulary and cognitive abilities will be assessed. This with the aim of analysing if there are any long-term effects of each intervention and infants continue learning words and potentially "catching up", or if the intervention programmes are only beneficial while they are being implemented. The cognitive assessments will be used to assess whether the intervention has an effect on visual spatial skills and working memory. In both cases, it will be done by comparing the infants results to the standardized mean of UK infant population. Similarly, infant's result in the follow up language assessment will be compared to the standarized mean of UK infant population.

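### The one-year language comparison with the UK mean, on a receptive test not given at entry, cannot show catching up or attribute it to either intervention

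*Combined protocol and SAP*

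**What the plan says.** Objective C (section 3.1) is a primary objective: the effect on language and cognition at one year, compared with the specific word intervention. Section 3.3 lists both receptive and expressive language as one-year outcomes.

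Section 4.4 names one language test for that visit: "The British Picture Vocabulary Scale (BPVS3) will be used to assess receptive language". No expressive test is listed there.

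Section 6.3.2 gives the aim as finding out "if there are any long-term effects of each intervention and infants continue learning words" and possibly catch up, or whether the benefit lasts only as long as the programme. For the cognitive tests, "it will be done by comparing the infants results to the standardized mean of UK infant population". For language, the infant's "result in the follow up language assessment will be compared to the standarized mean of UK infant population". It names no test, cut-off, change score or between-arm contrast for the follow-up.

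At entry, language is measured by parent checklist: "In the first and last session, parents/guardians will also be asked to fill in the UK-CDI Words and Gestures questionnaire" (section 4.3.1). Section 6.3.1 takes the numbers of words understood and produced from that checklist; these "will be considered as the baseline language ability before the intervention programme".

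Section 1.2 defines Late Talkers by limited expressive language. It adds that some catch up, "but others show persistent language difficulties throughout their lives".

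**The concern.** Catching up is a change in a child's position relative to peers. It needs a starting position on a comparable measure, and the plan has none for the follow-up language test. Attributing a change to an intervention needs a comparison between randomised arms, and section 6.3.2 gives none at one year although objective C asks for one.

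A primary long-term conclusion is at stake. If BPVS3 scores lie near the UK mean, the report could say the children caught up. If they lie below it, the report could say the programmes help only while they run. Neither statement would follow from the comparison described. Section 1.2 itself says some Late Talkers recover, so a good result in either arm could be natural course.

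**Working it through.** **Can a BPVS3 score at one year show change?** The relevant sections, side by side:

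| Item | Entry | One year | Section |
|---|---|---|---|
| UK-CDI checklist (words understood, words produced) | yes, and at the last session | not listed | 4.3.1, 4.4, 6.3.1 |
| BPVS3 (receptive) | not listed | yes | 4.3, 4.4 |
| WPPSI-IV | yes, week 2 | yes | 4.3.2, 4.4 |
| Expressive test | checklist only | promised in 3.3, none in 4.4 | 3.3, 4.4 |

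The missing entry value therefore concerns language, not cognition. Eligibility (section 4.1.1) is a moderate or severe language delay diagnosed by a therapist, with no receptive criterion.

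Work in norm-SD units and take a follow-up score of −0.5. Change = follow-up − entry:
- entry −1.5: −0.5 − (−1.5) = +1.0, a gain
- entry −0.5: −0.5 − (−0.5) = 0, no change
- entry 0: −0.5 − 0 = −0.5, a loss

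The same result fits all three, and nothing planned distinguishes them on this test.

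**Can it be attributed to an intervention?** No. The UK norm is not a randomised comparator. Both arms could sit at the norm, or below it, whatever either intervention did. This applies to the cognitive follow-up too, as section 6.3.2 describes it.

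**If the comparison is made on group means, what does non-significance tell us?** The plan gives no figure for this analysis to reproduce. Inputs:
- n = 24 completers and n = 30 recruited (section 6.1). Section 6.1 does not name the test behind the 24; it is used here only as a sample size.
- n = 12 = 24/2 per arm, assuming 1:1 allocation (ratio not stated).
- Norm mean 100, SD 15, two-sided 5% one-sample t-test: all assumed.

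P(non-significant) = P(|T| < t(0.975, n−1)), where T is noncentral t with n−1 degrees of freedom and noncentrality δ√n/15 for a true deficit of δ points. Example, n = 12 and δ = 10: noncentrality 10 × √12 / 15 = 2.31, critical value 2.201, probability 0.442.

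| n | 4.5 points below (0.3 SD) | 7.5 below (0.5 SD) | 10 below (0.67 SD) | 95% CI half-width |
|---|---|---|---|---|
| 12 | 84% | 65% | 44% | 2.201 × 15/√12 = 9.5 |
| 24 | 71% | 35% | 12% | 2.069 × 15/√24 = 6.3 |
| 30 | 64% | 25% | 6% | 2.045 × 15/√30 = 5.6 |

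The 30 row assumes no loss.

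**What would the between-arm contrast deliver?** With 12 per arm and SD 15, the unadjusted 95% CI half-width is 2.074 × 15 × √(2/12) = 12.7 points. The difference detectable with 80% power is 1.20 SD = 18 points. Adjustment for a covariate correlated 0.5 to 0.8 with the outcome lowers this to 1.04 to 0.72 SD, or 15.6 to 10.8 points. The documents do not give the correlation between the checklist count and BPVS3; it may be lower than 0.5.

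**The case against.** **The group mean and the significance test are inferred.** Section 6.3.2 speaks of the infant's result, and the only mean it names is the norm's. Section 6.3.1 uses similar wording for WPPSI-IV as a check on each participant. The t-tests in 6.3.2 are against chance in the noun extension task, and nowhere does the plan say that a non-significant difference from the UK mean will count as catch-up. This stands, so the table applies only if group means are tested. The other two arguments do not depend on it: a child-by-child comparison with the norm still has no entry value and no comparator arm.

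**A reader might infer that the mix of recovered and persistent children can never be shown.** The documents do not support that. Individual scores, or a count below a cut-off, could be reported from the data already planned; the plan sets no such summary.

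**A reader might also take the 15th percentile in section 1.2 as a ready recovery threshold.** It is not one for this test. The text reads "Late Talkers tend to be below the 15th percentile of expressive vocabulary", which describes expressive vocabulary, and BPVS3 is receptive.

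**Receptive vocabulary is measured at entry.** The count of words understood says something about early comprehension. It comes from a different instrument, so it cannot give a change score, but it can serve as a covariate.

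**The size of the problem depends on the grouping.** It does: a 10-point deficit is missed 44% of the time with 12 children but only 12% with 24 pooled. Pooling, however, gives up any comparison of the interventions.

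**Conclusion.** The concern holds in a limited form. As written, the follow-up language analysis cannot show catching up, because BPVS3 has no entry value and measures a domain in which delay was not required. Nor can it attribute anything to either intervention, because the comparator is a norm. Both conclusions follow from the documents without any assumed figure.

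The third part is conditional. If group means are tested against the norm, a deficit of 7.5 to 10 points is missed 65% to 44% of the time with 12 children, 35% to 12% with 24 and 25% to 6% with 30. This rests on SD 15, a two-sided 5% t-test, 1:1 allocation and no further loss by one year. The documents do not show that the sponsor intends to read non-significance as recovery; they leave that reading open.

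**What to change.** In section 6.3.2:

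1. Make the objective C language analysis the age-standardised BPVS3 score per arm with its 95% CI, and the between-arm difference with its CI, adjusted for the baseline UK-CDI count of words understood.
2. Present the comparison with the UK norm descriptively, showing individual scores. If a count below a cut-off is wanted, pre-specify the cut-off, report the number per arm, and label it a receptive convention, not the expressive threshold of section 1.2. Keep it descriptive: even 12 of 24 has a 95% CI of 31% to 69% (Wilson).
3. State that a non-significant difference from the UK mean will not be read as catch-up.
4. Call the result receptive vocabulary relative to the UK norm at one year.

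The cost is SAP wording only; every item uses data already planned. The downside is that estimates from about 24 children are imprecise and the long-term conclusion becomes more modest. These changes do not supply the expressive outcome promised in section 3.3. That would need an added measure, such as repeating the UK-CDI at follow-up.

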6.3.3 Secondary outcomes analysis

As mentioned before, a mixed effect model analysis will be conducted and two of the factors introduced in this model will be the attention measure and the sorting task. With this, we will assess the role of attention and sorting abilities in word learning with the objective of knowing if only infants with certain attention patterns and/or infants that are sensitive to shape similarities can develop a shape bias.

7 Data management

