3.2. Secondary objectives

As a secondary objective, the study will investigate whether some children are more receptive to the shape bias intervention programme than others. More specifically, we will:

- D. Assess whether the success of teaching Late Talkers a shape bias for noun extension is related to their sensitivity to object shape similarities.
- E. Assess whether the success of teaching Late Talkers a shape bias for noun extension is related to their ability of sustain their attention to novel objects that are presented to them.

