3.4. Secondary outcome measures

Objective D), i.e. whether children are more receptive to the shape bias intervention if they are sensitive to shape similarities, will be assessed by relating children's ability to sort objects by shape before the intervention and their ability to extend object labels by shape after the intervention.

Objective E), i.e. whether children' are more receptive to the shape bias intervention if they can sustain their attention to novel objects, will be assessed by relating children's sustained attention during the presentation of a video showing a person presenting and moving novel objects before the intervention, their attention to the novel objects during the intervention, and their ability to extend object labels by shape after the intervention.

4. Method

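### Objectives D and E ask which children respond better to shape training, but the plan names no arm-by-predictor term, and a factor averaged over both arms cannot tell receptiveness from a general tendency to choose by shape

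*Combined protocol and SAP*

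**What the plan says.** Section 3.2 sets the secondary question: "whether some children are more receptive to the shape bias intervention programme than others". Section 3.4 puts it into practice for objective D by "relating children's ability to sort objects by shape before the intervention and their ability to extend object labels by shape after the intervention". For objective E it relates attention to the pre-test video, "their attention to the novel objects during the intervention, and their ability to extend object labels by shape after the intervention". Neither statement is limited to one arm or asks for a comparison between arms.

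Section 6.3.2 gives the model: "The factors that predict the number of noun extensions based on shape as well as vocabulary growth will be assessed using mixed effect model analyses". Besides baseline vocabulary, the factors listed are "the intervention type (shape training vs specific word training), attention measures (pre-test and attention during training), and sorting task measure". Both arms are therefore in the fit. Section 6.3.3 adds only that "two of the factors introduced in this model will be the attention measure and the sorting task".

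Four other points bear on this:

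- Both arms take identical generalization tests (section 4.2).
- The assessments before training are the vocabulary checklist, the questionnaire, the sorting task, the attention task and the WPPSI-IV (sections 4.3.1 and 4.3.2). None is a noun-extension test.
- Sorting is recorded in four categories: shape, colour, texture or no preference (section 6.3.1 D).
- The comparison arm is trained on real common objects (section 4.3.3.2).

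**The concern.** Receptiveness to a training programme means that its effect, the difference between arms, varies with a baseline trait. That is an arm-by-trait contrast. A single coefficient for sorting or attention, fitted beside intervention type, answers a different question: whether the trait goes with shape choices on average across trained and untrained children.

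If children who sort by shape also tend to pick the same-shape toy at week 9 whatever their training, the pooled coefficient is positive although training worked no better in them. It could then be read as support for the proposition that only "infants that are sensitive to shape similarities between objects can acquire a shape bias". If the association exists in one arm only, the pooled coefficient is roughly half of it and does not show which arm it came from. With no noun-extension score before training, the specific-word arm is the only reference for a general tendency to choose by shape. The listed factors do not use it that way for D and E.

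The attention predictor has a further difficulty. Section 3.4 refers to "their attention to the novel objects during the intervention", while section 6.3.2 lists attention during training for a model of both arms. The specific-word arm handles familiar kinds of object, so the measure would mean different things in the two arms. It is also taken after randomisation. One common coefficient is hard to interpret.

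**Working it through.** **The plan's own figure.** The plan gives no calculation for D or E. Its only sample-size figure is 24 completers for power 0.8, a medium effect and error probability 0.05 (section 6.1), with no test named. A two-group comparison at d = 0.5 needs 2 × (1.96 + 0.84)² / 0.5² ≈ 63 per arm. A repeated-measures ANOVA with f = 0.25, two groups, four measurements and correlation 0.5 gives 24 in total. The figure is thus neither confirmed nor refuted, and nothing below depends on it beyond using 24 as the number analysed.

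**Inputs.** From the plan: 24 completers, two randomised arms, the same test in both. Assumed, because the documents give no values: 1:1 allocation (12 per arm), a standardised continuous predictor, residual SD 1, and the slopes below.

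**What each term estimates.** Let b_S and b_W be the slopes of shape choices on the predictor in the shape and specific-word arms. With equal arms and a predictor balanced by randomisation:

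- pooled factor ≈ (b_S + b_W) / 2
- interaction = b_S − b_W

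| b_S, b_W | Pooled | Interaction | Interaction significant (simulated) |
|---|---|---|---|
| 0.6, 0.6 | (0.6 + 0.6)/2 = 0.60 | 0 | 5% |
| 1.2, 0 | (1.2 + 0)/2 = 0.60 | 1.2 | 70% |
| 0.6, 0 | (0.6 + 0)/2 = 0.30 | 0.6 | about 25% |
| 0, 0.6 | (0 + 0.6)/2 = 0.30 | −0.6 | about 25% |

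The simulation fitted ordinary least squares with and without the interaction, and its mean pooled coefficients agree with the arithmetic. Rows 1 and 2 are opposite truths with the same pooled coefficient. So are rows 3 and 4.

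**Sensitivity to the assumed slope.** With equal slopes in both arms, so no differential response, the pooled factor is significant in about 15%, 27% and 73% of runs for slopes of 0.2, 0.3 and 0.6.

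**Would a shape-arm slope do instead?** No. Tested within the interaction model, it is significant in about 46% of runs under both (0.6, 0.6) and (0.6, 0). It does not use the comparison arm, so it cannot tell these apart.

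**Four-category sorting.** An arm-by-sorting term has (4 − 1) × (2 − 1) = 3 df. With equal category frequencies (an assumption) and 12 children, the chance that an arm has an empty category is 4 × 0.75¹² − 6 × 0.5¹² + 4 × 0.25¹² = 0.125. For at least one empty cell in either arm it is 1 − (1 − 0.125)² = 0.23. The chance that some cell holds at most one child is 81%. Shape versus other is easier to estimate but not safe: if 10% of children prefer shape (assumed), the shape cell is empty in at least one arm with probability 1 − (1 − 0.9¹²)² ≈ 0.49; at 25% it is 1 − (1 − 0.75¹²)² ≈ 0.06.

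**Size needed for the interaction.** By normal approximation, 80% power needs about 126, 50 and 32 children in total for slope differences of 0.5, 0.8 and 1.0.

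**The case against.** Several points on the other side stand.

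- A reader might infer that the plan rules out an interaction. It does not. Section 6.3.2 gives no model formula and presents its list as the most important factors, not all of them. The interaction is unspecified. But it is the term that answers D and E, it is absent from the section written for them, and left open it could be chosen after seeing the data.
- A reader might infer that D and E are bound to get a wrong answer. That is too strong. Section 3.4 describes D as relating two measures, and a pooled coefficient does estimate an association. When the association exists only in trained children, the coefficient is diluted but keeps its sign. The difficulty is that the result cannot be read as receptiveness, the word used in sections 3.2 and 3.4.
- The 73% rests on one assumed slope. Nothing in the documents gives a slope in untrained children. The background says Late Talkers lack a shape bias, and section 4.3.2 says that sorting by shape is demonstrated to the child, so the slope could be small.
- A reader might infer that attention during training does not exist in the specific-word arm. Section 6.3.2 lists it without that restriction. What differs is its meaning, and sections 3.4 and 6.3.2 do not describe it alike.
- The plan poses whether only certain infants can acquire the bias as a question. It does not commit to that conclusion.
- The sample is small for interactions. This is true, and it argues for estimates with intervals and an exploratory label. It does not make the pooled factor an answer to the question.

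**Conclusion.** The point holds as a gap between the secondary objectives and the analysis named for them. The factors in sections 6.3.2 and 6.3.3 estimate an association averaged over arms. Without a noun-extension test before training, that average cannot distinguish receptiveness to the shape programme from a general tendency to choose by shape. The structural result, that the pooled term is the mean of the two slopes and the interaction is their difference, needs only roughly equal arms and a balanced predictor. The percentages rest on assumed slopes, residual SD 1, 12 per arm and a continuous predictor; they illustrate the size and do not predict it. The point affects secondary objectives only and should be corrected before analysis.

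**What to change.** In section 6.3.3, for the week-9 shape-choice score:

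1. Add an arm-by-pre-test-attention term.
2. In a separate model, add an arm-by-sorting term, with sorting coded in advance as shape preference versus other or as a count of shape-based sorts. The count avoids empty cells if few children prefer shape.
3. Base D and E on the interaction estimate with its 95% CI. Show the association within each arm as description only.
4. Report attention to novel objects during training as a descriptive association within the shape arm, and state that it cannot by itself show receptiveness. Align the wording of sections 3.4 and 6.3.2 on this measure.
5. Label these analyses exploratory, and do not conclude that only certain infants can acquire a shape bias.

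This needs no new visits, tests or children: it is SAP wording and one extra term per model. The downside is imprecision. At 24 children, power is about 25% for a slope difference of 0.6, and lower if dichotomising sorting discards information. The plan should say so.

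### Attention and sorting terms in a mixed model cannot show that 'only' attentive or shape-sensitive infants acquire a shape bias

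*Combined protocol and SAP*

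**What the plan says.** All references are to the combined protocol and SAP.

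- **Section 6.3.2** models noun extension by shape and vocabulary growth with mixed effect models. The main factors are baseline words, intervention type, attention (before and during training) and sorting. Of the output it says: "It will also assess the role of attention in word learning and whether only infants that pay attention to novel items" and, later in the same sentence, "infants that are sensitive to shape similarities between objects can acquire a shape bias".
- **Section 6.3.3** says that "two of the factors introduced in this model will be the attention measure and the sorting task", "with the objective of knowing if only infants with certain attention patterns and/or infants that are sensitive to shape similarities can develop a shape bias".
- **Section 6.3.1**, on attention: "This variable will be registered as a continuous variable and used as a predictor of the primary outcome measures". It gives no cut-off for an attentive infant. Sorting is a four-level category (shape, colour, texture, none).
- **Comparison with chance** (6.3.2) is by t-tests on the response pattern, with no breakdown by attention or sorting.
- **Sections 3.2 and 3.4** put objectives D and E more mildly. Section 3.2 asks whether success is related to the trait; section 3.4 asks "whether children are more receptive to the shape bias intervention if they are sensitive to shape similarities".

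No trait-by-arm term is named, and no rule is given for concluding 'only'.

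**The concern.** The question in 6.3.2 and 6.3.3 is one of necessity: can an infant who attends little, or does not sort by shape, still acquire the bias? To answer yes or no, one must know whether such infants choose by shape more often than chance. A coefficient for attention or sorting answers a different question, namely whether shape choices differ with the trait. Rejecting 'no difference' shows that infants with more of the trait do better. It leaves open whether the others learned less or learned nothing.

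At stake is the reading of objectives D and E. A significant term could be reported as showing that other Late Talkers cannot be taught a shape bias when they were taught it, only less strongly. A non-significant term could be reported as showing that the trait is not needed.

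**Working it through.** The plan gives no figure on this point, so there is none to reproduce. The core argument is logical; the calculations show how it plays out at this sample size.

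**Inputs from the document.** Three objects per trial (4.3.4, same procedure in 4.3.5), so chance is 1/3. Four pairs of objects at week 9 (4.3.5), so 4 or 8 trials per infant, the number not being stated. 24 completers, or 30 recruited (6.1).

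**Assumptions.** 1:1 allocation (4.2 gives no ratio), so 24/2 = 12 to 30/2 = 15 shape-arm infants. The true shape-choice rates, the spread of attention and the between-infant SD are also assumed. A linear model of per-infant proportions stands in for the unspecified mixed model.

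**Step 1. How often does a graded effect give a significant term?** Each infant's shape choices are Binomial(k, expit(a + b·z + 0.5·u)), with z the standardised attention score and u a standard normal infant effect. Infants at −1 SD of attention are truly at 0.50, above 1/3. There are 12 infants per arm, controls are at 1/3, and 20,000 replicates were run. The table gives the share of trials with a positive slope at two-sided p < 0.05.

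| True rate at +1 SD | Shape arm, k=4 | Shape arm, k=8 | Both arms pooled, k=4 | Both arms pooled, k=8 |
|---|---|---|---|---|
| 0.70 | 19% | 29% | 13% | 18% |
| 0.80 | 39% | 57% | 22% | 33% |
| 0.90 | 64% | 84% | 37% | 50% |

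With no gradient the share is about 2.5%. Because z and u are normal, about 4% to 7% of shape-arm infants in these scenarios are truly below 1/3, so not quite every infant learns. Step 2 removes that feature.

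**Step 2. Can the term tell the two truths apart?** Here every trained infant lies between 0.50 and 0.90 (graded), or the less attentive half is at 1/3 and the rest at 0.80 (only). There are 12 or 15 trained infants, 8 or 16 trials, no further between-infant variation, and 5,000 runs per case.

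| Check | Graded: all learn | Only the attentive half learns |
|---|---|---|
| Attention term, shape arm alone | 62% to 96% significant | 92% to 100% significant |
| Attention term, both arms, controls at 1/3 | 31% to 61% | 56% to 87% |
| Less attentive half of shape arm tested above 1/3 | 80% to 99% | about 2% |

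A significant term is common under both truths. A non-significant term is no clearer: in the pooled model with 'only' true, it occurs in 100 − 87 = 13% to 100 − 56 = 44% of runs. The comparison with 1/3 is what separates the cases.

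**Step 3. Does it matter which model supplies the low-attention estimate?** Take shape-arm infants at −1 SD truly at 1/3, those at +1 SD at 0.80, controls at 1/3, 8 trials and 12 infants per arm.

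- An additive model over both arms gives a mean fitted low-attention rate of about 0.47, and its lower 95% limit exceeds 1/3 in about 33% of runs.
- A fit to the shape arm alone gives about 0.36, and the limit exceeds 1/3 in about 5% of runs.

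The flat control arm dilutes the slope and pushes the low-attention estimate upward. Conversely, if attention matters only in controls (1/3 to 0.60, trained infants flat at 0.70), the pooled term is significant and positive in 16% to 32% of runs.

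**Step 4. Could this sample support 'only'?** Take 6 low-trait infants, 8 trials and within-infant correlation 0.2.

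- Child SD = √(0.25 × (1 + 7 × 0.2)/8) = √0.075 = 0.274.
- SE = 0.274/√6 = 0.112.
- With t(5) = 2.571, the 95% half-width is 2.571 × 0.112 = 0.29.

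At p = 1/3 the variance term is 2/9 in place of 0.25. The SD is then √(0.0667) = 0.258 and the half-width 2.571 × 0.258/√6 = 0.27. A group observed exactly at chance would have an upper limit of 0.33 + 0.27 = 0.60, so substantial learning could not be excluded.

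**The case against.** The case on the other side is substantial, and much of it stands.

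- *No decision rule is stated.* A reader might infer that the plan equates a significant term with 'only', and a non-significant one with 'not needed'. The document does not say so; it says the model will assess the question. What stands is a risk of misreporting, not a planned error.
- *The percentages are not error rates.* A reader might take the figures in step 1 as false-positive rates and set them against 2.5%. They are not: a true gradient exists in those scenarios, and the test detects it correctly. They show only how often a finding open to the 'only' reading would arise. Sorting was not simulated.
- *The objectives are already worded well.* Sections 3.2 and 3.4 ask about association, which the model suits. True, and it places the fault in 6.3.2 and 6.3.3. But 'only' appears in both, each time as what the analysis is for.
- *The model may yield rates by sorting category.* A four-level factor does give category estimates, so a reader should not infer that no such estimate could exist. However, no comparison of them with 1/3 is stated, and without a trait-by-arm term they are not specific to shape training.
- *The t-tests may be split by trait.* Section 6.3.2 is silent on grouping. That silence does not establish a split.
- *Harm to children.* A reader might infer that the programme would be withheld from some children. No section ties these secondary results to such a decision.

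**Conclusion.** The point holds as a mismatch between a stated conclusion and a stated analysis. Attention and sorting terms can show that some infants are more receptive. They cannot show that the rest stay at chance, and no stated analysis examines that. This rests on logic and on reading a model term in the usual way, as a test of association, since the plan gives no null hypothesis for these factors.

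Its size is modest: a risk of over-claiming on secondary objectives D and E. With less attentive infants also learning, a significant term would occur in about 13% to 84% of trials, depending on the assumed gradient, the number of trials per infant and whether the arms are pooled. Those figures depend on assumed true rates, an infant SD of 0.5 on the logit scale, 12 infants per arm and a linear approximation.

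The subgroup comparison with 1/3 is informative but not decisive. With 4 to 8 infants, 4 to 16 trials, true rates of 0.45 to 0.50 and the same infant SD, its power to detect above-chance learning is only about 10% to 66%. Failure to exceed chance would therefore not prove 'only' either.

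**What to change.** 1. In 6.3.2 and 6.3.3, replace the 'only' wording with the question in 3.4: whether infants with higher attention, or who sort by shape, are more likely to extend names by shape after shape training.
2. Estimate this in the shape arm alone, or add attention-by-arm and sorting-by-arm terms. An additive model over both arms should not supply these estimates, for the reason shown in step 3.
3. From that fit, report the week-9 shape-choice rate with a 95% confidence interval for shape-arm infants at low attention (a level fixed in advance, for example the lower quartile) and for those who do not sort by shape, each set against 1/3.
4. State that neither a significant nor a non-significant factor establishes or refutes 'only', and that this sample is unlikely to support an 'only' claim.

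The cost is rewording two sentences, specifying the fit and adding two reported estimates. No new data, visits or participants are needed. The downside is a weaker permitted claim and wide intervals from about 12 to 15 shape-arm infants, assuming 1:1 allocation.
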